3. STUDY DESIGN

3.1 OVERVIEW OF STUDY DESIGN

This is a 12-week double-blind, placebo-controlled, parallel-group, multicenter, proof-of-concept study to assess the effect of 12-week administration of ESN364 in early postmenopausal women suffering from hot flashes.

[figure not shown]
A total of 80 subjects are planned to be included in the study, i.e., 40 subjects in the active treatment arm and 40 subjects in the placebo arm. Each subject will be administered an oral dose of 90 mg ESN364 b.i.d. or placebo b.i.d., as per pregenerated randomization list.

The study will consist of a screening period of maximum 4 weeks and a 12-week double-blind treatment period (Weeks 1-12), followed by a follow-up visit 2-3 weeks after the last study drug intake.

The study will be performed on an ambulatory basis. During the treatment period, subjects will be asked to come to the clinical site every 4 weeks (Day 1 and Weeks 4, 8, 12; Visits 2-5).

A schematic overview of the study design is shown in [Figure 5](#). The assessments performed are summarized per visit in the [Time and Events Schedule](#).

Figure 5: Schematic Overview of the Study

^a Screening is to be performed within 4 weeks prior to the first intake of study drug, with a minimum of 7 days to allow for baseline data collection of Hot Flash Score and Hot Flash Frequency.

An interim analysis on the primary endpoint, DEXA parameters and safety data will be performed once the first 16 subjects will have completed 12 weeks of treatment and the follow-up visit (or have discontinued earlier). The final analysis will be performed once all subjects will have completed 12 weeks of treatment and the follow-up visit (or have discontinued earlier).

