Blood samples for clinical laboratory tests will be taken at every visit and should be taken in a fasted state (overnight fast for at least 10 hours) for unbiased glucose, insulin, and C-peptide determination. Physical examination and vital sign assessments will also be made at every visit. An ECG will be recorded at every visit except Visit 4. Levels of the bone density markers BALP and CTX will be assessed at Visits 2 and 5 only.

DEXA will be repeated at Visit 5, before the last dose of the study drug. For practical reasons, the timing of DEXA may vary from the actual time of the visit, depending on the DEXA availability (DEXA appointment). The Visit 5 DEXA can be performed ± 4 days from the actual time of Visit 5. It is however to be performed before the last dose of the study drug; in case the DEXA appointment related to Visit 5 is scheduled later in time than Visit 5, study drug intake must be continued until DEXA has been performed (study drug intake at home and recorded in the ePRO diary).

Adverse events and concomitant therapies will be collected from signing of informed consent onwards (screening) through the follow-up visit.

Compliance towards study drug intake and ePRO completion will be checked at every visit during the treatment period. Compliance towards study drug intake will be assessed by counting returned dosage units in addition to ePRO entries. Any discrepancies between returned dosage units and dosing in the ePRO diary will be discussed with the subject for whom a discrepancy was seen.

An overview of the assessments to be performed during the treatment period is also provided in the [Time and Events Schedule](#).

7.1.3 *Follow-up Period (Visit 6)*

Two to 3 weeks after the last intake of the study drug, subjects will be asked to come to the clinical site for a follow-up visit.

An overview of the assessments to be performed at the follow-up visit is provided in the [Time and Events Schedule](#).

7.1.4 *Unscheduled Visits*

Unscheduled visits can be planned for instance:

- to obtain additional information to ensure safety to the subject. Additional blood and urine samples may be taken at the discretion of the Investigator.

- to collect an additional blood sample for PK assessment if a subject discontinues the study drug due to an AE;

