Any change in physical examination occurring during the study that is considered to be clinically relevant by the Investigator should be recorded in the source documents and the AE section of the eCRF.

7.5.2 *Safety Endpoints*

Safety endpoints are:

- AE frequency and severity from first dose of study drug through the last visit;
- Changes from baseline over time in hematology and biochemistry concentrations;
- Changes from baseline over time in vital sign and ECG assessments;
- Changes from baseline over time in BALP and CTX levels.

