9.1.5 Safety Data

Safety parameters will be tabulated and analyzed descriptively.

Adverse Events

The original terms used in the source documents and the designated sections of the eCRFs by the Investigator to identify AEs will be fully described and coded according to the Medical Dictionary for Regulatory Activities (MedDRA).

The reported AEs will be allocated to phases based on their start date. All AEs will be listed. All AEs with onset during the treatment phase (i.e., TEAEs) will be summarized by treatment arm by System Organ Class (SOC) and Preferred Term (PT).

Special attention will be paid to those subjects who died, discontinued the study drug due to an AE, or experienced a severe or serious AE. Summaries, listings, and narratives (also see Section 12.11) may be provided, as appropriate.

Clinical Laboratory Tests

Each continuous biochemistry and hematology laboratory test will be evaluated by means of descriptive statistics on the actual values, at each assessment time point and by treatment arm. Changes from baseline will be summarized by assessment time point and by treatment arm.

Laboratory tests will be categorized according to the normal ranges of the clinical laboratory (below, within, or above normal). A shift table versus baseline will be created. The worst post-baseline value will be summarized as well.

A listing of subjects with any clinical laboratory test result outside the normal range of the clinical laboratory will be provided.

Vital Signs

Body temperature, pulse rate, SBP, and DBP will be evaluated by means of descriptive statistics (actual values and changes from baseline) and shift tables according to the normal ranges (as defined in [Attachment 7](#)) at each assessment time point and by treatment arm.

Electrocardiogram

Electrocardiogram variables will be evaluated by means of descriptive statistics (actual values and changes from baseline) and shift tables according to the normal ranges (as defined in [Attachment 7](#)) at each assessment time point and by treatment arm.

The ECG variables that will be analyzed are HR, PR interval, QRS interval, QT interval. Values for QTc will be derived. QTcF will be the primary correction parameter [\[31\]](#). Categorical assessment will be performed on absolute QTcF interval prolongation (>450, >480, >500 ms) and on changes from baseline (increase >30 and >60 ms).

Physical Examination

Abnormal findings in physical examination will be listed.

9.1.6 *Interim Analysis*

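### The AE endpoint runs from first dose through the last visit, but the only by-arm AE table that Section 9.1.5 specifically commits to covers treatment-phase onset

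*Protocol*

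**What the plan says.** **Endpoint.** Protocol Section 7.5.2, and the synopsis in the same words, gives the AE endpoint as "AE frequency and severity from first dose of study drug through the last visit".

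**Design.** Section 3.1 describes a "12-week double-blind treatment period (Weeks 1-12), followed by a follow-up visit 2-3 weeks after the last study drug intake". Section 7.1 treats the two parts separately: 7.1.2 covers the treatment period (Visits 2-5, Weeks 1-12) and 7.1.3 the follow-up period (Visit 6).

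**Collection.** Section 7.1.2 states: "Adverse events and concomitant therapies will be collected from signing of informed consent onwards (screening) through the follow-up visit". The Time and Events Schedule also marks AEs at Visit 6.

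**Analysis.** Section 9.1.5 says: "The reported AEs will be allocated to phases based on their start date. All AEs will be listed". It then says: "All AEs with onset during the treatment phase (i.e., TEAEs) will be summarized by treatment arm", by System Organ Class (SOC) and Preferred Term (PT). For subjects who died, stopped the study drug because of an AE, or had a severe or serious AE, it adds: "Summaries, listings, and narratives (also see Section 12.11) may be provided, as appropriate". It does not say where the treatment phase ends.

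**The concern.** The endpoint and the table that should report it use different windows. Sorting AEs into phases by start date serves a purpose only if events outside the treatment phase are handled differently, and the table then takes the treatment phase alone. On a plain reading, an AE that starts after the last dose counts towards the endpoint but does not enter the one by-arm AE table the section specifies.

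What is at stake is the between-arm view of events that start after treatment, including those soon after an early stop. Section 1.5 calls knowledge of the side effect profile still limited. Section 1.3 reports that the single serious AE in the Phase I study, a foot fracture, arose during follow-up. That says nothing about cause, but it shows that such events occur. The data will be collected here in any case, so only the tabulation is in question.

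**Working it through.** **Inputs.** Screening is at most 4 weeks, treatment 12 weeks (84 days) and follow-up 2 to 3 weeks (14 to 21 days) after the last intake (synopsis; Sections 3.1 and 7.1.3). There are 40 subjects per arm (Section 3.1).

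**The plan's own figure.** Maximum involvement = 4 + 12 + 3 = 19 weeks, which matches the synopsis. The endpoint's last visit is therefore the follow-up visit.

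**Windows side by side, completer**

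| | Start | End | Length |
|---|---|---|---|
| Endpoint (7.5.2) | first dose | Visit 6 | 12 + 2 = 14 to 12 + 3 = 15 weeks |
| By-arm table (9.1.5), phase read as Weeks 1-12 | first dose | Week 12 | 12 weeks |

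Share of the endpoint window outside the table = f / (12 + f), with f the follow-up in weeks:
- f = 2: 2/14 = 14.3%
- f = 3: 3/15 = 20.0%

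**Early stop (illustration).** For a subject who stops at Day 28, with the phase ending at last intake, the share is 14/42 = 33% to 21/49 = 43%.

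**Subjects affected.** The protocol gives no rate of follow-up-onset AEs, so the proportion p of subjects with at least one is an assumption. The expected number per arm is 40p, and the chance of at least one in an arm is 1 - (1 - p)^40.

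| Assumed p | Expected per arm | Chance of at least one |
|---|---|---|
| 1% | 0.4 | 33% |
| 2% | 0.8 | 55% |
| 5% | 2.0 | 87% |
| 10% | 4.0 | 99% |

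**Do other outputs cover the gap?**
- The listing in 9.1.5 covers all AEs but is not a summary by arm.
- The summaries for deaths, AE discontinuations, and severe or serious AEs have no phase limit but are optional.
- The narratives in Section 12.11 are also optional. They cover all deaths, but the item for other serious AEs is limited to those during treatment.

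**Where the phase ends.** Sections 7.1 and 7.1.2 let the Visit 5 DEXA fall up to 4 days after Visit 5, with dosing continuing until then. An end at Week 12 and an end at last intake can therefore differ for the same completer.

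**The case against.** The strongest reply is that the end of the treatment phase is not stated, and that Section 9.1 leaves methods to a SAP that is not shown. The SAP could extend the phase to Visit 6. This stands as a limit on certainty: reading the phase as Weeks 1-12 is an inference, though the one the protocol's own division into periods supports. It does not remove the point, because the protocol itself states both the endpoint window and the table's scope, and the two do not match as worded. A SAP that extended the phase would be making the correction asked for here.

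A reader might infer that follow-up AEs drop out of every by-arm table and are never compared. The documents do not support that. Section 9.1 says in general terms that all collected data will be documented in summary tables, figures and listings. Section 9.1.5 opens with a general commitment to tabulate safety parameters, and its optional summaries have no phase limit. Naming one table does not exclude others.

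A reader might also take 14-20% as the share of AEs lost. It is a share of time, and equals a share of AEs only if onset is constant across the window. For drug-related events after stopping, that is doubtful. Mean half-lives in Section 1.3 run from 2.39 to 7.06 hours, so five half-lives take about 12 to 35 hours, and most of the 14 to 21 days passes with little drug present. Delayed or withdrawal events remain possible.

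Two further replies are fair. Laboratory tests, vital signs and ECG are scheduled at Visit 6 and summarised by arm at each time point, so follow-up safety is not otherwise missing. A main AE table restricted to treatment-emergent onset is also a common choice, and nothing here argues for dropping it.

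**Conclusion.** The mismatch holds. The by-arm AE table specifically committed to in Section 9.1.5 does not, as worded, deliver the endpoint in Section 7.5.2. If the treatment phase means the 12-week treatment period, the table leaves out 14% to 20% of a completer's endpoint window, and more for a subject who stops early. The number of AEs this represents cannot be derived from the protocol. At assumed rates of 1% to 10% of subjects it would be 0.4 to 4 subjects per arm.

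The consequence is modest. AE analysis is descriptive, follow-up AEs are still collected and listed, and no test, sample size or error rate depends on the wording. It is worth correcting because the two statements concern the same endpoint and the data needed will already be in hand.

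**What to change.** In Section 9.1.5:

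1. State where the treatment phase ends for allocating AEs, including for subjects who stop early and those who keep dosing past Visit 5 while awaiting DEXA.
2. Keep the on-treatment TEAE table.
3. Add that AEs with onset from first dose through Visit 6 are also summarised by arm, SOC and PT, split by treatment and follow-up phase, so that the analysis matches Section 7.5.2.

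The cost is a short text change and a few extra descriptive tables from the same programs. The counts over the full window will be slightly higher than on treatment alone. No new data collection is needed.

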9.2 DETERMINATION OF SAMPLE SIZE

As this study is only the first proof-of-concept Phase IIa study in this therapeutic area, no formal power calculations have been done. All the statistical analyses involving testing for significance will be exploratory in nature and will serve as a basis for designing and powering a subsequent (dose-ranging) Phase IIb study.

One (and actually the main reason) for the absence of such power calculation is the fact that this study is unprecedented. There are no references available that can give an indication of observed effect size of NK3 antagonism on Hot Flash Score and Hot Flash Frequency.

In a review article by Sloan et al. [22], the authors propose the following general guideline regarding set-up of studies using hot flash diary data (severity and frequency):

- For Phase III placebo-controlled studies, 50 patients per treatment arm seem appropriate to provide sufficient power specifications to detect a clinically meaningful change in hot flash activity.
- For Phase II trials, 25 patients per study seem to provide reasonable estimates of eventual hot flash efficacy to screen potential agents for more definitive testing.

Since the review article typically considers paroxetine and hormones, we would, in our specific case, expect the effect size to be larger and would therefore propose to be sufficiently powered to conduct a successful Phase II proof-of-concept study, while leaving some room for drop-outs and interim analysis.

10. ADVERSE EVENT REPORTING

10.1 DEFINITIONS

Adverse Event

An AE is any untoward medical occurrence in a clinical study subject administered a medicinal (investigational or non-investigational) product. An AE does not necessarily have a causal relationship with the study drug. An AE can therefore be any unfavorable and unintended sign (including an abnormal finding), symptom, or disease temporally associated with the use of a medicinal (investigational or non-investigational) product, whether or not related to that medicinal (investigational or non-investigational) product.

This includes any occurrence that is new in onset or aggravated in severity or frequency from the baseline condition, or abnormal result of diagnostic procedures, including clinical laboratory test abnormalities.

Serious Adverse Event

An SAE is any untoward medical occurrence that at any dose meets any of the following conditions:

- results in death;
- is life-threatening, i.e., the subject was at risk of death at the time of the event (e.g., ventricular fibrillation and anaphylaxis). The term does not refer to an event which hypothetically might have caused death if it were more severe.
- requires inpatient hospitalization or prolongation of existing inpatient hospitalization:
Hospitalization refers to an overnight admission into hospital for the purpose of investigating and/or treating the AE. Hospitalization for an elective procedure, or routinely scheduled treatment for a pre-existing condition that has not worsened, is not an SAE.
- results in persistent or significant disability/incapacity, i.e., causing substantial disruption of the subject's ability to conduct normal life;
- is a congenital anomaly/birth defect;
- is medically significant, i.e., may not be immediately life-threatening or result in death or hospitalization but may jeopardize the subject's health or may require intervention to prevent one of the above outcomes. Examples of such events are intensive treatment in an emergency room or at home for allergic bronchospasm, blood dyscrasias, or convulsions that does not result in hospitalization or development of drug dependency or drug abuse.

Unlisted (Unexpected) Adverse Event

An AE is considered unlisted if the nature or severity is not consistent with the applicable product reference safety information (see Investigator's Brochure [\[14\]](#)).

10.2 INTENSITY OF ADVERSE EVENTS

The severity of each AE must be rated as follows:

Grade 1:

Mild; asymptomatic or mild symptoms; clinical or diagnostic observations only; intervention not indicated.

Grade 2:

Moderate; minimal, local or non-invasive intervention indicated; limiting age-appropriate instrumental activities of daily life (preparing meals, shopping for groceries or clothes, using the telephone, managing money, etc.).

Grade 3:

Severe or medically significant but not immediately life-threatening; hospitalization or prolongation of hospitalization indicated, disabling; limiting self-care activities of daily life (bathing, dressing and undressing, feeding self, using the toilet, taking medications, and not bedridden).

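### The compulsory AE severity scale stops at a Grade 3 that, on its natural reading, excludes life-threatening and fatal events, so these have no valid grade in the AE-severity endpoint

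*Protocol*

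**What the plan says.** Protocol section 10.2 (Intensity of Adverse Events) opens with an instruction that allows no exceptions: "The severity of each AE must be rated as follows". Three grades follow:

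- The lowest, Grade 1, covers mild events that need no intervention.
- The middle level, Grade 2, is described as "Moderate; minimal, local or non-invasive intervention indicated; limiting age-appropriate instrumental activities of daily life".
- The highest, Grade 3, is described as "Severe or medically significant but not immediately life-threatening". The text goes on to mention hospitalization, disability and limits on self-care, and closes its list of self-care examples by specifying that the subject is not bedridden.

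Section 10.3 (Causality Assessment) comes next. There is no Grade 4 or 5.

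Section 10.1 (Definitions) includes among its criteria for a serious adverse event that it "results in death" or that it "is life-threatening, i.e., the subject was at risk of death at the time of the event", and gives ventricular fibrillation and anaphylaxis as examples of the latter. Section 10.5 (Outcome) has six outcome codes, one of which is Fatal.

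Section 7.5.2 (Safety Endpoints) names as its first endpoint "AE frequency and severity from first dose of study drug through the last visit". Section 9.1.5 (Safety Data) gives special attention to subjects who died, who stopped study drug because of an AE, or who "experienced a severe or serious AE".

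**The concern.** A severity scale that must be applied to every event should have a place for every event the protocol expects to record. Here the scale is closed at the top by its own wording, while the same chapter foresees events beyond that limit. An investigator who follows section 10.2 to the letter has no correct answer for a life-threatening or fatal event. Two investigators could handle the same situation differently, one leaving the field blank and the other entering Grade 3 despite the definition.

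Severity is half of the first-listed safety endpoint, and it is rated at the site under the protocol. A statistical analysis plan can decide how to tabulate the grades, but it cannot supply a category that the investigator was never offered. The point is therefore not one that the protocol can leave to that document.

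**Working it through.** No figure is at issue, so the check is textual: take the two kinds of event that section 10.1 foresees and try each grade of section 10.2 in turn.

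1. **Is there a counterpart to the exclusion in Grade 3?** The life-threatening criterion in 10.1 requires actual risk of death at the time of the event and sets aside events that might hypothetically have caused death. That is the same idea as an immediate threat to life, so the criterion in 10.1 and the exclusion in 10.2 concern the same events.

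2. **Fit of each grade.**

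| Event foreseen in 10.1 | Grade 1 | Grade 2 | Grade 3 |
|---|---|---|---|
| Life-threatening | No: requires that no intervention is indicated | No: requires only minimal, local or non-invasive intervention | No on the natural reading: excluded by the opening phrase, and often by the bedridden wording |
| Results in death | No, for the same reason | No, for the same reason | No on the natural reading: a fatal event lies beyond one that poses no immediate threat to life |

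 Of the 3 grades, 0 fit either kind of event.

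3. **Is there a rule elsewhere that closes the gap?** Sections 7.5.1.1, 9.1.5 and 10.1 to 10.8, together with Attachment 6, contain no second AE severity scale and no rule that assigns life-threatening or fatal events to Grade 3. Section 10.5 codes death as an outcome, which is a separate attribute from intensity.

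4. **Where is the rating used?** In the endpoint in 7.5.2, and in the reference to severe AEs in 9.1.5. Section 9.1.5 specifies summaries of treatment-emergent AEs by arm, System Organ Class and Preferred Term. It does not define a table by severity, so the form in which the gap would show is not fixed in the protocol.

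5. **How many events could be affected?** The endpoint runs from first dose to last visit, which is 12 weeks of treatment plus 2 to 3 weeks, or 14 to 15 weeks. With 80 women and no early withdrawal:
 - 80 × 14 = 1,120 woman-weeks, and 1,120 / 52 ≈ 21.5 woman-years
 - 80 × 15 = 1,200 woman-weeks, and 1,200 / 52 ≈ 23.1 woman-years

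 About half of this is on active treatment. Section 1.3 reports no deaths and one subject with a severe treatment-emergent event, on placebo, among the 65 subjects of the Phase I study. The documents give no expected rate of life-threatening or fatal events, so no count can be calculated. These figures suggest that it is small.

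**The case against.** The strongest reply is that little depends on the grade. A life-threatening or fatal AE is serious by definition (10.1), is recorded on the AE form (10.6) and is reported within 24 hours (10.7). Death has its own outcome code (10.5), and narratives are foreseen for deaths and other serious events on treatment (12.11). Section 9.1.5 names deaths first and covers every life-threatening event through the word serious, so these subjects receive special attention whatever grade they are given. All of this stands. A reader might infer that such events could drop out of the safety data, or that all of them would be missing from a severity table. The documents do not support either inference: capture does not depend on the grade, and the protocol defines no such table.

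A second reply is that the qualifier in Grade 3 may attach only to medically significant events, leaving severe events unrestricted. Section 10.1 lends this some support, because its medically significant criterion is also described as possibly not immediately life-threatening. The reading is arguable, but section 10.2 does not state it, and it does not explain the bedridden wording. A scale that can be read both ways still needs rewording.

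A third reply is that three levels are a legitimate choice. That is correct. A reader might object that a fatal event would then share a class with a self-limiting severe one. That is not a defect here, because an open-ended Grade 3 would do the same and is an acceptable solution, given that death and threat to life are coded elsewhere. The fault is the limit placed on the top level, not the number of levels.

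**Conclusion.** Wrong as written, and minor. Section 10.2 requires a grade for every AE and, on its natural reading, provides none for life-threatening or fatal ones, although 10.1 and 10.5 foresee them. The consequence is limited to the severity rating and the severity half of the endpoint in 7.5.2, where such an event would be ungraded or graded against the definition. Capture and expedited reporting of serious events, the fatal outcome code, the review of deaths and serious events, and the primary efficacy endpoint are all unaffected.

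The conclusion rests on reading the Grade 3 qualifier as covering the whole opening phrase. On the narrower reading the gap shrinks to an ambiguity and to the bedridden wording, and the same edit resolves it. The low expected number of events rests on the size and length of the trial and on the Phase I experience, not on a stated rate. Section 1.5 itself calls knowledge of the side-effect profile still limited.

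**What to change.** Make one of two edits to section 10.2:

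- **Extend the scale.** Keep Grade 3 as it is and add a category for life-threatening AEs and one for fatal AEs. The wording should also settle where a bedridden subject whose life is not in danger belongs.
- **Open the top grade.** Keep three grades, delete the phrase that excludes immediate threat to life, and clarify or remove the bedridden wording, so that Grade 3 takes every event worse than Grade 2.

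Either edit makes 10.1, 10.2, 10.5 and 7.5.2 agree. The cost is about two lines of protocol text. If the eCRF code list mirrors section 10.2, the first option also needs two more entries there, and the second needs none beyond any help text that repeats the definition. The eCRF was not available to check. Neither option affects dosing, visits, sample size or stopping rules.
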